7.7.2 Post-randomisation evaluations

Adverse event (AE) reporting checks will be made by a delegated member of the research team at the day 3-5 assessment, between day 10-12, on the final day of study treatment and at day 30 post randomisation. Patients enrolled into the study will also be under continuous clinical observation as part of their routine direct clinical care. The site PI or delegate will liaise with the clinical team on a daily basis and a telephone number will be provided as a direct point of contact with the research team for discussion of any concerns relating to the study or administration of the study drug. Any adverse events noted outside the prespecified reporting checks will be processed.

Details of each administration of study drug will be recorded in the case report form (CRF) and the clinical drug administration record. This will include details of administration site, date and time of administration.

A second research blood sample will be taken at 3-5 days post randomisation for measurement of plasma inflammatory markers (IL-6) (putative mediator) and IL-1Ra concentration (treatment fidelity and validation of randomisation). Further clinical data (survival check; detail of target aneurysm, including confirmation, position and treatment) will be collected at the day 3-5 post randomisation assessment.

On the final day of study treatment another survival check will be performed. As part of the end of treatment assessment the participants will be asked to confirm their willingness to be contacted at 30 days and 6 months of the date of randomisation and contact details of the participants (or next of kin) will be confirmed.

A final AE check and survival check will be performed at 30 days post randomisation on all patients who have received at least one dose of study drug and will be completed by local research staff. To avoid

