9.1.1 Operational definitions for (S)AEs

The safety reporting period will commence from the time of consent, and will continue up to 30 days from date of randomisation.

Given the nature of aSAH these participants will have experienced a number of AEs which are disease related. A list of expected events related to normal disease progress is detailed in **Table** 4. However this does not mean that these events should always be attributed to SAH. All events should be assessed for causality by the investigator. There is no requirement to capture disease-related AEs that occur during the trial in the CRF but all disease-related AEs should be recorded in the patient's medical notes. AEs that are un-related to SAH should be recorded in the CRF. Pre-existing conditions (i.e. those that already appear in the medical notes) do not qualify as adverse events unless they worsen. If the PIs suspect this worsening is related to study drug then this event should be treated as an AR.

AEs will be classified as detailed in **Table 3**.

All AR's occurring during the trial whether observed by the investigator or reported by the participant will be captured in the patient's medical notes and CRF.

All SAEs which occur within the safety reporting period will be captured in the patient's medical notes, CRF and expediently reported as detailed in section 9.2.

Any new ARs, SAEs or AEs that are unrelated to SAH occurring after discharge but within 30 days from date of randomisation will be recorded in the patient's CRF and will be considered as potentially related to study drug.

Any ARs, SAEs or AEs unrelated to SAH that are still on-going at the time of the final AE check (30 days post randomisation), the participant may be followed up for a longer period of time until the event has resolved, stabilised or has been fully investigated to the satisfaction of the PI and the study Sponsor. To capture the outcome of these on-going AEs, this may require contact with the participant's general practitioner and other health care practitioners involved in the participant's on-going clinical care following discharge from the recruiting site. The GP/other healthcare providers will have been informed of the patient's study participation and they will be provided with a copy of the participant's consent which details this clause of contact to be made.

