Any new AEs, ARs or SAEs which occur after 30 days from randomisation will not be sought or recorded in the CRF. They will be recorded in the patient's medical records if considered necessary for clinical care. If an investigator becomes aware of any drug-related SARs that occur after the end of safety reporting period (30 days post randomisation) these must also be reported to the Manchester CTU within the expedited timelines (please see section 9.2).

Reporting of any AE will be performed in line with MHRA guidelines and the Sponsor's requirements. The following attributes will be assigned where known: description, dates of onset and resolution; severity; assessment of relatedness to study drug administration; meets criteria of serious (Y/N); action taken and treatment required. If treatment for the event was administered it will be recorded in the medical record.

The PI or medical delegate at the recruiting centre will be responsible for assessing any AE on the following characteristics: seriousness, relationship to the study drug, expectedness and severity. AEs severity will be reported to the definitions detailed in table 3 below. Assessment of expectedness will be made against the current approved version of the SmPC.

Table 3: Assessment of Severity

SCALE	SEVERITY	DEFINITION
1	Mild	Aware of sign / symptom but easily tolerated
2	Moderate	Discomfort enough to cause interference with usual activity
3	Severe	Incapacitating, unable to work or perform usual tasks
4	Life-threatening	Risk of death at time of event
5	Fatal	Death ensues

The PI or delegate will determine whether there is a **reasonable possibility** that the study drug has caused or contributed to an event, based on clinical judgment and available information on the study drug from the SmPC. Factors taken into account will include, but not be limited to, the following:

- A temporal relationship between the event and administration of the study drug
- A plausible biological mechanism for the study drug to cause the event
- Previous report of similar AEs associated with the study drug, in accordance with the SmPC
- Recurrence of the AE after re-challenge or resolution after discontinuation of study drug

Sponsor & IDMC will continue to monitor SAEs for trends and possible signal detection associated with study drug.

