9.2 Recording and Reporting of SAEs, SARs AND SUSARs

All SAEs, SARs and SUSARs occurring from the time of written informed consent until 30 days from date of randomisation must be recorded on the Serious Adverse Event/Reaction Form and emailed to the Manchester CTU immediately but no later than 24 hours of the research staff becoming aware of the event. The research staff should also report any SAE occurring after this time period which they believe to be related to the study drug.

All SAEs must be reported by email immediately but no later than 24 hours of being aware to the SCIL trial manager at the Manchester CTU.

Email: [contact]

In addition to events that meet the SAE criteria detailed in section 9.1, the following 'important medical events' should be reported as SAEs:

- A diagnosis of new or recurrent Tuberculosis
- A diagnosis of new cancer
- Any suspected transmission of an infectious agent via study drug shall also be considered serious.

Exceptions that will not be subject to expedited reporting include:

- Extended hospitalisation for treatment of underlying condition
- Routine treatment or monitoring of SAH not associated with any deterioration in condition.
- Treatment which was elective or pre-planned, for a pre-existing condition including SAH provided that the SAH is not associated with any deterioration in condition, e.g. pre-planned hip replacement operation which does not lead to further complications or insertion of shunt.
- Treatment on an emergency, outpatient basis for an event not fulfilling any of the definitions of serious as given above and not resulting in hospital admission
- Admission to hospital or institution for another life circumstance that has no bearing on health status e.g. lack of housing, caregiver respite, family circumstances.

For each SAE, SAR & SUSAR the following information will be collected:

- full details in medical terms and case description
- event duration (start and end dates, if applicable)
- action taken
- outcome
- seriousness criteria
- causality (i.e. relatedness to study drugs), in the opinion of the investigator
- whether the event would be considered expected or unexpected.

All SAEs that occur within safety reporting period (consent until 30 days from date of randomisation) should be considered for their potentially relatedness to study drug.

Protocol V7.20 Sep 2019

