9.5 Notification of Deaths

All deaths that occur within 30 days of the date of randomisation will be reported as SAE as per pharmacovigilance section to the Manchester CTU. This report will be within 24h of the research team becoming aware. In addition, all deaths will be recorded in the CRF up to 6 months post randomisation.

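### The last scheduled adverse event and survival check may fall on days 27 to 29, so up to three days of the 30-day safety period are covered only passively

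*Protocol*

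**What the plan says.** The reporting period is tied to the date of randomisation. Section 9.1.1: "The safety reporting period will commence from the time of consent, and will continue up to 30 days from date of randomisation". The same section closes it: "Any new AEs, ARs or SAEs which occur after 30 days from randomisation will not be sought or recorded in the CRF". Section 11.3.3 plans safety analyses over the same 30 days, in the aneurysmal population and in the full randomised cohort.

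The last check is tied to a visit. Section 7.7.2: "A final AE check and survival check will be performed at 30 days post randomisation on all patients" who have had at least one dose. That section and section 9.1.1 give it no window, but the Table 1 column heading allows 3 days either side. The month 6 column of Table 1 holds the outcome questionnaires and a survival check, and no adverse event check.

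Duties that do not depend on the visit date also apply:
- Section 9.2: "All SAEs, SARs and SUSARs occurring from the time of written informed consent until 30 days from date of randomisation must be recorded".
- Section 9.1.1, on new reactions, serious events and events unrelated to the haemorrhage: those "occurring after discharge but within 30 days from date of randomisation will be recorded in the patient's CRF".
- Section 7.7.2: "Any adverse events noted outside the prespecified reporting checks will be processed".
- Section 9.5: "all deaths will be recorded in the CRF up to 6 months post randomisation".

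Under section 7.8, participants withdrawn because no aneurysm was confirmed are followed only to the 30-day safety assessment.

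**The concern.** The period to be reported and analysed has a fixed end, while the contact that closes it may come up to three days sooner. The two halves of the window are not alike. A contact on days 31 to 33 loses nothing, because the participant can be asked about everything up to day 30 and later events are out of scope. A contact on days 27 to 29 leaves days about which no one is scheduled to ask.

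For someone still in the neurosurgical unit this matters little, because clinical observation continues. For someone discharged home, the telephone call is the planned way for the site to learn of events. For participants without a confirmed aneurysm it is also the last scheduled survival check, although they count in the full-cohort safety analysis. Rebleed, CSF diversion, delayed cerebral ischaemia and CSF infection are completed at the same assessment, so an early contact shortens their planned ascertainment too.

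What is at stake is the completeness of the 30-day safety counts. The primary outcome is not affected.

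**Working it through.** The protocol gives no figure to reproduce. The check is date arithmetic, in whole days from randomisation (day 0).

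**Inputs**
- Nominal day and window of the safety contact: day 30, plus or minus 3 days (Table 1).
- End of the reporting period: day 30 (sections 9.1.1 and 9.2).
- Later scheduled adverse event checks: none (Table 1; section 7.7.2 calls this check the final one).
- Latest dosing: day 21 from ictus, with the first dose within 72 hours of ictus (section 7.4).
- Five half-lives of the drug: 30 hours (section 7.2.1).
- Planned recruitment 1000, with about 20% expected to have no aneurysm (sections 11.1 and 11.7).

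**Range of compliant contact days**
- Earliest: 30 − 3 = day 27. Latest: 30 + 3 = day 33.

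**Days with no scheduled check** = max(0, 30 − contact day)
- Day 27: 3 days, 3/30 = 10% of the period.
- Day 28: 2 days, 2/30 = 6.7%.
- Day 29: 1 day, 1/30 = 3.3%.
- Days 30 to 33: 0.

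**Average over all participants**

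This needs the spread of contact days, which the protocol does not give. The possible range is 0 days (nobody contacted early) to 3 days (everybody on day 27). As an illustration only, assume contacts spread evenly over the seven allowed days:
- Share contacted early: 3/7 = 43%.
- Mean loss among those contacted early: (3 + 2 + 1)/3 = 2 days.
- Mean loss over all participants: (3 + 2 + 1)/7 = 0.86 days, and 0.86/30 = 2.9% of the period.

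**Participants with no later scheduled contact**
- 20% × 1000 = about 200. Only those of them contacted on days 27 to 29 are affected.

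**Where the gap lies relative to treatment**
- Randomised on the day of ictus: last dose by day 21 from randomisation, so day 27 is at least 27 − 21 = 6 days later.
- Randomised three days after ictus: last dose by day 18, so at least 27 − 18 = 9 days later.
- Both far exceed 30 hours.

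**After the change**

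If the contact cannot fall before day 30, the formula gives 0 for every compliant contact. On day 30 itself, only the remaining hours of that day are left.

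**The case against.** A reader might infer that days 28 to 30 are uncovered for participants contacted early, that nothing is sought after the visit, or that only death is recovered. The protocol does not support this. The sentence in section 9.1.1 cuts off events that occur after day 30, not events after the contact. Serious events to day 30 must be reported whatever the visit date, post-discharge events within 30 days go in the CRF, and events noted outside the scheduled checks are processed. Under section 9.10, events at the day 30 assessment that may be drug-related lead to further contact. Section 9.5 records all deaths to 6 months without restricting this to aneurysmal cases. This part of the objection stands: the days remain reportable, and only active ascertainment is missing.

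A reader might also assume that most participants are home by then. The protocol gives no length of stay, and it provides for in-patients and for transfers to rehabilitation centres or district hospitals. The gap can be claimed only for those discharged, in unknown number.

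The likely yield of these days is low as well. They fall at least 6 days after the last dose, section 1.1.1 places delayed cerebral ischaemia most commonly between days 4 and 10, and disease-related non-serious events need not enter the CRF. Section 11.3.3 does not say how observation time will be handled, so no error in the analysis itself can be asserted. A symmetric window is also ordinary practice. All of this limits the size of the point.

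It does not remove it. The remaining duties work only if the site becomes aware of an event, and for a discharged participant the contact is the planned route to that. For participants without a confirmed aneurysm, section 9.5 states a duty to record deaths, but section 7.8 leaves no scheduled contact at which one would be found.

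**Conclusion.** The point holds as a minor mismatch. The Table 1 window lets the last scheduled adverse event and survival check precede the end of the safety period by up to three days, and in those days capture is passive. This mainly concerns discharged participants, and particularly those without a confirmed aneurysm.

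The loss is at most 3 of 30 days per participant contacted early. Averaged over everyone it would be about 0.86 days (2.9%) if contacts were spread evenly, an assumption with no source in the protocol. Lost days are not lost events, and the number of events missed cannot be estimated from the document. Because the trial is blinded and both arms follow one schedule, the loss is not expected to differ by arm. It would slightly understate 30-day event counts without favouring either treatment. The case for acting is that the correction is very cheap.

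**What to change.** In Table 1, replace the 3-days-either-side window for this contact with one that cannot open before day 30. Two options:
- 0/+6 days (days 30 to 36) keeps the present seven-day width.
- 0/+3 days (days 30 to 33) keeps the present latest date but narrows the window to four days.

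State that the questions, the survival check and the aneurysm-related items cover the time up to and including day 30. Put the same window and wording in sections 7.7.2 and 9.1.1, and adjust the CRF date check.

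No extra contact is needed. The cost is slightly longer recall and later reports for some participants: up to 3 days beyond the present latest date with 0/+6, and none beyond it with 0/+3, although sites then have fewer days in which to reach people. Serious event reporting, which runs from the site's awareness, does not change. If early contacts must stay allowed, a second contact on or after day 30 for those participants would also close the gap, at the price of an extra call.

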9.2 Recording and Reporting of SAEs, SARs AND SUSARs

All SAEs, SARs and SUSARs occurring from the time of written informed consent until 30 days from date of randomisation must be recorded on the Serious Adverse Event/Reaction Form and emailed to the Manchester CTU immediately but no later than 24 hours of the research staff becoming aware of the event. The research staff should also report any SAE occurring after this time period which they believe to be related to the study drug.

All SAEs must be reported by email immediately but no later than 24 hours of being aware to the SCIL trial manager at the Manchester CTU.

Email: [contact]

In addition to events that meet the SAE criteria detailed in section 9.1, the following 'important medical events' should be reported as SAEs:

- A diagnosis of new or recurrent Tuberculosis
- A diagnosis of new cancer
- Any suspected transmission of an infectious agent via study drug shall also be considered serious.

Exceptions that will not be subject to expedited reporting include:

- Extended hospitalisation for treatment of underlying condition
- Routine treatment or monitoring of SAH not associated with any deterioration in condition.
- Treatment which was elective or pre-planned, for a pre-existing condition including SAH provided that the SAH is not associated with any deterioration in condition, e.g. pre-planned hip replacement operation which does not lead to further complications or insertion of shunt.
- Treatment on an emergency, outpatient basis for an event not fulfilling any of the definitions of serious as given above and not resulting in hospital admission
- Admission to hospital or institution for another life circumstance that has no bearing on health status e.g. lack of housing, caregiver respite, family circumstances.

For each SAE, SAR & SUSAR the following information will be collected:

- full details in medical terms and case description
- event duration (start and end dates, if applicable)
- action taken
- outcome
- seriousness criteria
- causality (i.e. relatedness to study drugs), in the opinion of the investigator
- whether the event would be considered expected or unexpected.

All SAEs that occur within safety reporting period (consent until 30 days from date of randomisation) should be considered for their potentially relatedness to study drug.

Protocol V7.20 Sep 2019

Any change of condition or other follow-up information should be emailed to the Manchester CTU using the Follow-up Form as soon as it is available but no later than 24 hours of the information becoming available. All serious adverse events will be followed up until the event resolves, stabilises or a final outcome has been reached.

Initial assessment of seriousness, causality and expectedness will be made by the PI or delegated doctor at the recruiting centre. If an authorised doctor from the reporting site is unavailable, initial reports without causality will be submitted to the Manchester CTU by a healthcare professional immediately but no later than 24 hours after of becoming aware of the SAE, but must be followed-up by medical assessment as soon as possible thereafter.

Assessment of seriousness, causality and expectedness will be reviewed by the CI against the current approved version of the SmPC. If a difference of opinion exists between the investigator and CI regarding causality, the event cannot be downgraded by the CI as the investigator is more familiar with the participant's history, clinical signs and symptoms, lab findings and other investigations. The CI may, however, upgrade the investigator's assessment of causality.

All SAEs assigned by the CI or delegate (or following central review) as both **suspected** to be related to study drugs **and unexpected** will be classified as SUSARs and will be subject to expedited reporting to the Medicines and Healthcare Products Regulatory Agency (MHRA). The Manchester CTU will inform the MHRA, the REC and the Sponsor of SUSARs within the required expedited reporting timescales.

9.3 Responsibilities

The Trial Steering Committee (TSC) will be responsible for overseeing the management of the study and its conduct. They will be responsible, in conjunction with the Chief Investigator for determining whether the study should stop. However, the overall responsibility for the decision to continue or stop will remain with the Sponsor.

The constitution, responsibilities and remit of the TSC and IDMC for the study will be in keeping with the recommendations and guidance of the NIHR & Sponsor (full details of the TSC can be found in section 10.2.2). The role, functions and operating practices of the TSC and the IDMC will be agreed with the NIHR & Sponsor before the commencement of recruitment.

The IDMC will undertake clinical review of a line listing of all life threatening or SAEs resulting in death each month and a cumulative review of all unblinded safety information on a 12 monthly basis. The total numbers of SAEs per month will be sent to the IDMC Chair – in order to expedite a safety review if more SAEs are being seen than would be expected.

Table 5: Responsibilities relating to AE reporting

	PI / recruiting centre	CI	Manchester CTU	
Adverse event	 Identification of adverse event Assessment of seriousness Assess if appropriate for expedited reporting Complete AR log in the CRF and send to the Manchester CTU within 30 days of safety assessment visit Follow-up until resolution or stabilisation 	• Clinical oversight of the safety	 Central data collection and processing of AEs, ARs, SAEs, SARs and SUSARs according to the trial protocol. Reporting safety information to the CI, delegate or independent clinical reviewer for the ongoing assessment of the risk / benefit. Reporting safety information to 	
Serious adverse event / SARs	Ensure all necessary care and including immediate support necessitated by the event has been implemented Complete SAE form Assessment of seriousness, expectedness, & causality Submit SAE/SAR form to the Manchester CTU immediately but no later than 24 hours of the research staff becoming aware of the event Follow-up until resolution or stabilisation	of patients participating in the trial, including an ongoing review of the risk / benefit. • Using medical judgement in assigning seriousness, causality and expectedness of SAEs where it has not been possible to obtain local medical assessment. • Using the approved SmPC in assigning expectedness. • Immediate review of all SUSARs.	of patients participating in the trial, including an ongoing review of the risk / benefit. • Using medical judgement in assigning seriousness, causality and expectedness of SAEs where it has not been possible to obtain local medical assessment. • Using the approved SmPC in assigning expectedness. • Immediate review of all SUSARs. • Review of specific SAEs and SARs in accordance with the trial risk assessment and	committees identified for the trial (Data Monitoring Committee (DMC) and / or Trial Steering Committee (TSC)) according to the Trial Monitoring Plan. • Expedited reporting of SUSARs to the Competent Authority (MHRA in UK) and REC within required timelines. • Notifying Investigators of SUSARs that occur within the
SUSARs	 Ensure all necessary care and including immediate support necessitated by the event has been implemented. Complete SAE form Assessment of seriousness & causality. Submit SAE/SAR form to the Manchester CTU immediately but no later than 24 hours of the research staff becoming aware of the event. Confirm with CI drug reaction and unexpected. Follow-up until resolution or stabilisation. 	 Assigning Medical Dictionary for Regulatory Activities (MedDRA) or Body System coding to all SAEs and SARs. Preparing the clinical sections and final sign off of the Development Safety Update Report (DSUR). 	 Record details of event. Request further information if needed. Generate a detailed adverse event monthly report. Ensure follow up information is completed to outcome. Ensure information passed on to DMC, MHRA, Sobi within regulatory timescales. 	

IDMC	TSC	
Monthly clinical review of safety reports.		
•In accordance with the Trial Terms of Reference for the IDMC, periodically reviewing unblinded overall safety data to determine patterns and trends of events, or to identify safety issues, which would not be apparent on an individual case basis.	•In accordance with the Trial Terms of Reference for the TSC, periodically reviewing safety data and liaising with the IDMC regarding safety issues.	
• Recommend continuation or suspension of trial to TSC		
Discuss with TSC if recruitment should be suspended	•Confirm continuation of recruitment	

Safety monitoring will be undertaken by the IDMC. They may recommend suspending or terminating recruitment on the grounds of safety, but will not extend the study. The decision to suspend or terminate the study remains the responsibility of the CI and the study sponsor.

